## LIST OF ABBREVIATIONS

AE	adverse event
CAINS	Clinical Assessment Interview for Negative Symptoms
CFR	Code of Federal Regulations
CRF	case report form
DMC	Data Monitoring Committee
DSMB	Data Safety Monitoring Board
DSM-V	Diagnostic and Statistical Manual of Mental Disorders, 5 th Edition
FACES	Facial Expression Coding System
FDA	Food and Drug Administration
fMRI	Functional Magnetic Resonance Imaging
GCP	Good Clinical Practice
HIPAA	Health Insurance Portability and Accountability Act of 1996
ICF	informed consent form
ICH	International Conference on Harmonisation
IEC	Independent Ethics Committee
IRB	Institutional Review Board
IU	International Unit
OT	Oxytocin
PI	Principal Investigator
rTPJ	Right Temporal Parietal Junction
SAE	Serious Adverse Experience
SFS	Social Functioning Scale
ToM	Theory of Mind

## PROTOCOL SYNOPSIS

TITLE	A pharmaco-imaging approach to predicting social functioning and clinical responses to oxytocin administration in schizophrenia
SPONSOR	[name]., Ph.D.
FUNDING ORGANIZATION	VA Clinical Science Research and Development Program
NUMBER OF SITES	2
RATIONALE	
The purpose of this project is to investigate the neural mechanisms of oxytocin's (OT) prosocial effects in patients with schizophrenia. Schizophrenia is a prevalent disorder that severely impacts social function in affected individuals – it deprives patients of precious relationships, undermines lifelong occupational function, and causes great stress for families and caregivers. Current treatments for schizophrenia are inadequate and have substantial side effects. Thus, novel pharmacologic interventions that target key neurophysiological deficits in the disease are desperately needed.
 
Patients with schizophrenia have significant social cognitive deficits including impaired theory of mind (ToM; i.e., impaired understanding of other peoples' mental states) as indexed by poor recognition of facial emotion [1],[2]. These deficits interfere with social relationships, impact community functioning, and are more common and more strongly associated with quality of life and functional outcomes than "positive" symptoms such as hallucinations and delusions, and "cold cognition" such as executive functioning and working memory.
 
Abnormal neural responses underlie these social deficits. Current antipsychotic medications are ineffective at treating social deficits, improving social functioning, or normalizing neural responses in patients with schizophrenia. However, oxytocin, a neuropeptide involved in attachment, parenting, and sociality in mammals, has promise as a treatment for these deficits. Intranasally administered oxytocin is safe for humans and has prosocial and beneficial neurophysiological effects in healthy and patient populations. The investigators propose to use functional magnetic resonance imaging (fMRI) to elucidate the neural mechanisms of oxytocin's prosocial effects on critical social cognitive processes. These experiments will:
 
 
1) Provide high-impact data on how oxytocin affects neural mechanisms that underlie social cognition in healthy individuals and in patients with schizophrenia; and
 
2) Lead to a deeper understanding of how to intervene to improve functioning in these neural systems.
 

STUDY DESIGN	This is a double-blind, placebo-controlled, counterbalanced order with a cross-over design one week apart, followed by a randomized,

	double-blind, three week (18-24 days) study design. We will also be implementing a response adaptive randomization (RAR) design after the first 60 participants complete the study. This will change the allocation ratio to favor the drug treatment arm with greater improvement in social functioning, while keeping adequate statistical power in all arms.
PRIMARY OBJECTIVE	The objective is to clarify how and in whom exogenous oxytocin improves social functioning in schizophrenia as measured by acute neural response patterns during social cognitive tasks and social functioning as measured by the Social Functioning Scale (SFS).
SECONDARY OBJECTIVES	
Social skills will be assessed during the chronic period over the phone or video chat. Participants will answer questions about their social interactions and experiences.
 
Theory of Mind (ToM) will be assessed using the Hinting Task a well validated audiovisual tool that incorporates social interferences.
 
Negative symptoms will be assessed with Clinical Assessment Interview for Negative Symptoms (CAINS), comprising two subscales reflecting the negative symptom factors. Data will be analyzed with manual and computerized approaches.

NUMBER OF SUBJECTS	100 total participants
SUBJECT SELECTION CRITERIA	
Inclusion Criteria:
 
18-70 years of age; meet DSM-V criteria for schizophrenia, schizoaffective disorder or brief psychotic disorder; no medication changes or psychiatric hospitalizations in the past month; SFS raw score of no more than 75.
 
Exclusion Criteria:
 
Active substance use disorder in the past month except mild to moderate cannabis use disorder, schizoaffective, schizopreniform disorder, or brief psychotic disorder; DSM-5 diagnosis other than schizophrenia; Significant neurological/medical disorders; a pacemaker; extensive dental work; claustrophobia; deafness; inability

	to read; current participation in a psychosocial intervention; taking high dose testosterone, estrogen/progesterone. Currently pregnant, breastfeeding, or unwilling to practice birth control during participation.
TEST PRODUCT, DOSE, AND ROUTE OF ADMINISTRATION	fMRI phase: Single dose 40 IU of intranasal oxytocin  Longitudinal phase: Twice-daily for approximately 3 weeks (18- 24 days) of 40 IU of intranasal oxytocin
CONTROL PRODUCT, DOSE AND ROUTE OF ADMINISTRATION	fMRI phase: Single dose of intranasal placebo  Longitudinal phase: Twice-daily for approximately 3 weeks (18-24 days) of intranasal placebo
DURATION OF SUBJECT PARTICIPATION AND DURATION OF STUDY	
Subjects will be on study for up to 42 days
 
Screening: The investigators will contact subjects to conduct a phone screening interview to verify eligibility. Screening will take at most twenty minutes. In order to reduce number of in-person visits, Visit 1 has been adapted to be completely remote. Participants will verbally consent at the start of Visit 1, before completing any study tasks or assessments. Clinical diagnosis will be obtained prior to participation and will take up to 4 hours.
 
Written informed consent will be obtained during Visit 2, the first in-person visit, before study drug administration.
 
Treatment: Subjects will participate in the study for up to 7 weeks. The first two visits will be separated by at least 1 week. The third and fourth visit will be separated by at least 3 weeks (18-24 days). Each visit will be between one to four hours.
 
The total duration of the study is expected to be 5 years. 54 months for subject recruitment.

CONCOMITANT MEDICATIONS	
Allowed: atypical antipsychotic medication of a consistent, therapeutic dose
 
Prohibited: high dose testosterone or estrogen/progesterone

EFFICACY EVALUATIONS	The epidemiologist will be evaluating social functioning at multiple points throughout the study to determine the drug treatment arm with greater improvement which will then be implemented in the RAR design. Results will remain blinded to the study staff.
PRIMARY ENDPOINT	
 
• Neural activity from fMRI
 

	
 
• Social Functioning Scale (SFS)
 

SECONDARY ENDPOINTS	
 
• Social Skills
 
• Negative Symptoms
 
• Theory of Mind
 

OTHER EVALUATIONS	
SAFETY EVALUATIONS	No serious adverse effects have been demonstrated in studies examining intranasal administration of OT in numerous patient and healthy populations. Therefore, we don't predict any serious adverse events to occur during this study. Documented side effects include runny, stuffy, or irritated nose, and more rarely, nausea and vomiting. Participants may experience distress due to the nature of personal questions about mental health, substance use, and life experiences. They may also experience anxiety and/or fatigue due to length of the study days.
PLANNED INTERIM ANALYSES	Interim analysis will be conducted after the first 60 participants have completed the study and at multiple points over the course of the study. Results will remain blinded to all other study staff.
STATISTICS Primary Analysis Plan	
Linear regression analyses with SFS change and rTPJ activation as the primary outcomes and drug modeled as a 2-level dummy variable comparing the study drug vs. placebo.
 
Similar analyses will be conducted for the secondary clinical outcomes including social ability, negative symptoms (CAINS and Theory of Mind (HintingTask).

Rationale for Number of Subjects	All power and effect size estimates were calculated using STATA/SE v. 15.1 using 80% power and two-sided alpha=0.05. To be conservative, the investigators used the one-way command with two or three groups. The proposed sample size of 100 participants enables us to detect effect sizes of 0.23 for the primary hypotheses, which is clinically meaningful.

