### **4 STUDY DESIGN**

#### **4.1 Study Overview**

100 subjects are planned. During the fMRI phase, intranasal oxytocin and placebo will be administered to each subject in a randomized, double-blind, counterbalanced order with a cross-over design, at least one week apart. Testing will commence 45 minutes after drug administration and continue for no longer than 3 hours.

During the longitudinal phase, participants will then be randomized to receive approximately three weeks (18-24 day range) of twice daily administration of either OT or placebo. Testing will commence on baseline and after three weeks (18 to 24 days) of drug administration.

Screening data will be reviewed to determine subject eligibility. Subjects who meet all inclusion criteria and none of the exclusion criteria will be entered into the study.

The following treatment regimens will be used:

- Experimental treatment: Intranasal oxytocin
- Placebo: Saline solution

Total duration of subject participation will be 15 hours over 2 months.

---

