## 8 STUDY TREATMENTS

### 8.1 Method of Assigning Subjects to Treatment Groups

Randomization sequences will be generated using a response adaptive randomization study design. Enrollment would end when at least 55 participants have been assigned to the drug treatment arm and 40 participants have been assigned to the placebo arm.

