### **12.2 Demographic and Baseline Characteristics**

### **12.3 Analysis of Primary Endpoint**

The investigators will perform linear regression analyses with SFS change as the primary outcome and drug modeled as a 2-level dummy variable (drug vs. placebo). Identical analyses will be run using accuracy scores for the FBT and PDT instead of rTPJ activity to determine if acute OT improves ToM ability versus placebo.

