### **12.6 Sample Size and Randomization**

All power and effect size estimates were calculated using STATA/SE v. 15.1 using 80% power and two-sided alpha=0.05. To be conservative, the investigators used the one-way command with two or three groups. The proposed sample sizes enable us to detect effect sizes ranging from 0.23 to 0.27 for the primary hypotheses, which are clinically meaningful and consistent with the preliminary data.

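### For SFS change, 100 participants give about 62% power at an effect size of 0.23 (read as Cohen's f), not the stated 80%; at the 55/40 enrollment minimum it is about 59%.

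*Combined protocol and SAP*

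**What the plan says.** The synopsis (Rationale for Number of Subjects) gives the settings: "All power and effect size estimates were calculated using STATA/SE v. 15.1 using 80% power and two-sided alpha=0.05". It adds that a one-way command with two or three groups was used, and describes this as conservative. It then concludes: "The proposed sample size of 100 participants enables us to detect effect sizes of 0.23 for the primary hypotheses, which is clinically meaningful".

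Section 12.6 repeats the settings but gives a range and no N: "The proposed sample sizes enable us to detect effect sizes ranging from 0.23 to 0.27 for the primary hypotheses". It calls these effects clinically meaningful and in line with preliminary data.

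The synopsis analysis plan names two primary outcomes, SFS change and rTPJ activation. They come from different designs:

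- **SFS change** comes from the longitudinal phase, where "participants will then be randomized to receive approximately three weeks (18-24 day range) of twice daily administration of either OT or placebo" (section 4.1). Section 12.3 plans "linear regression analyses with SFS change as the primary outcome and drug modeled as a 2-level dummy variable (drug vs. placebo") and names no covariate.
- **rTPJ activation** comes from the fMRI phase, where "intranasal oxytocin and placebo will be administered to each subject in a randomized, double-blind, counterbalanced order with a cross-over design" (section 4.1).

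Section 8.1 lets enrollment end once "at least 55 participants have been assigned to the drug treatment arm and 40 participants have been assigned to the placebo arm". The synopsis says the adaptive allocation will favour the better arm "while keeping adequate statistical power in all arms".

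**The concern.** One detectable effect is quoted for two primary endpoints, one measured between subjects and the other within subjects. A single figure is unlikely to suit both, and 0.23 looked too small for a two-arm parallel comparison of 100 people.

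SFS is the primary efficacy endpoint (section 5.1), and this sentence is the justification for its sample size. It tells an IRB or funder that an SFS effect called clinically meaningful would be missed one time in five. If the true risk is nearer two in five, a null SFS result would be read as stronger evidence against benefit than the design can supply.

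**Working it through.** **Inputs.** N = 100, 80% power, two-sided alpha 0.05, one-way method with k = 2 or 3 groups, effect 0.23 (synopsis); 0.23 to 0.27 (section 12.6); minimum allocation 55/40 (section 8.1). Withdrawals are to be replaced (section on replacement of subjects), so no dropout allowance is applied.

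**Assumption.** The documents do not name the metric. I read 0.23 as Cohen's f (SD of group means divided by within-group SD). For two equal groups f = d/2, so 0.23 is d = 0.46 in SDs of SFS change.

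**Formula.** Power = P(F′ > F crit), with F′ noncentral F on (k − 1, N − k) degrees of freedom and noncentrality λ = N·f². For unequal arms, λ = d²·n₁n₂/(n₁ + n₂).

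**1. Trying to reproduce 0.23 at N = 100.** λ = 100 × 0.23² = 5.29.

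| | k = 2 | k = 3 |
|---|---|---|
| Power at f = 0.23 | 62.5% | 51.4% |
| f detectable at 80% | 0.283 (d = 0.57) | 0.315 |
| N needed for f = 0.23 | 151 | 186 |

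The stated figure is not reproduced. Two groups is the more favourable reading. As a check, the normal approximation gives 63.3% power and 75 per arm (150 in total).

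**2. Allocation, with d held at 0.46.**

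| Arms | λ | Power | d at 80% |
|---|---|---|---|
| 50/50 | 0.2116 × 25.00 = 5.29 | 62.5% | 0.57 |
| 60/40 | 0.2116 × 24.00 = 5.08 | 60.7% | 0.58 |
| 55/40 | 0.2116 × 23.16 = 4.90 | 59.1% | 0.59 |

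Simulation of 100,000 trials each gave 62.3% (50/50) and 59.3% (55/40). With 95 participants split evenly, power is 60.2%. So of the 3.4-point drop from 50/50 to 55/40, about 2.3 points come from having five fewer participants and about 1.1 from imbalance.

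**3. Upper end of section 12.6.** At f = 0.27 (d = 0.54), two-group power is 76.2% at 50/50 and 73.0% at 55/40. That is still below 80%, if the range refers to this sample.

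**4. Other readings of 0.23 at N = 100, two groups.**

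| Reading | Power at 0.23 | 80% point on that scale |
|---|---|---|
| Cohen's d | 20.7% | 0.57 |
| Correlation (f = 0.23/√(1 − 0.23²) = 0.236) | 64.8% | above 0.23 |
| f² | 99.7% | 0.283² = 0.080 |
| η² | over 99.9% | 0.080/1.080 = 0.074 |
| f, one-sided alpha 0.05 (contrary to the text) | 73.9% | 0.250 |

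None makes 0.23 the 80% point.

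**5. rTPJ for comparison.** In a paired analysis the standardised mean difference is d_z = 0.46/√(2(1 − ρ)), where ρ is the within-subject correlation. The documents give no ρ, so a range is shown for 100 pairs: ρ = 0, d_z = 0.325, power 89.6%; ρ = 0.3, d_z = 0.389, power 97.1%; ρ = 0.5, d_z = 0.46, power 99.5%. With 95 pairs and ρ = 0, power is 88.1%.

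**The case against.** The strongest objection is that the result depends on an unnamed metric. Read as f² or η², an effect of 0.23 has over 99% power, so a claim that it can be detected would be literally true. But those are not the natural scales for a one-way command, and 0.23 would then be about three times the detection limit.

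The standardising SD is also unstated. If 0.23 is in SDs of the raw SFS score, a baseline-to-follow-up correlation of about 0.67 would bring power to 80%, because 0.46/√(2 × 0.33) = 0.57. Adjusting for a baseline covariate correlated about 0.6 with the outcome would also do it (80.8%). These routes are real, but neither the correlations nor the adjustment appears in the documents. A later SAP is promised, but the sentence has to stand on the inputs given with it.

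The primary hypotheses are not listed beside the power figure, so applying it to SFS is an inference. It is a safe one: the synopsis analysis plan names SFS change as a primary outcome. Section 3.1 also asks whether acute rTPJ response predicts clinical response, and no power figure is tied to that question.

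Two further points stand. Imbalance itself costs only about one point of power, so the adaptive allocation is not the main problem. And all figures here are for a fixed design: they leave out the repeated interim analyses (section 12.5) and the response-adaptive allocation.

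**Conclusion.** The concern holds. For SFS change, the stated method with 100 participants gives 62.5% power at 0.23 rather than 80%. The chance of missing that effect is about 38%, or 41% at 55/40, instead of 20%. The effect detectable with 80% power is f = 0.283 (d = 0.57), or d = 0.59 at 55/40.

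This rests on reading 0.23 as Cohen's f in SDs of SFS change, with two groups, no covariate adjustment and a fixed design. The sentence needs correcting on every metric tried, because none puts the 80% point at 0.23 with N = 100. The shortfall is confined to SFS; rTPJ analysed as a paired cross-over comparison would have about 90% power or more at the same effect.

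On the f scale, two groups with N = 150 detect 0.230 and three groups with N = 135 detect 0.270. The published figures may therefore belong to other sample sizes, but the documents do not confirm this. The correction is necessary because this is the sample-size justification for the primary efficacy endpoint.

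**What to change.** Restate power by endpoint in the synopsis and section 12.6. The sponsor should first confirm which metric and SD the 0.23 refers to. If it is Cohen's f on SFS change, the SFS text could read:

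*With 100 participants in two equal arms and two-sided alpha 0.05, the comparison of SFS change has 80% power at f = 0.28 (d = 0.57), or at d = 0.59 if enrollment stops at 55 and 40. Power at d = 0.46 (f = 0.23 with equal arms) is about 62% and 59% respectively. These figures do not allow for interim analyses or adaptive allocation.*

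In addition:

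- Give rTPJ power separately as a paired cross-over comparison, with its assumed within-subject correlation.
- For each figure, name the metric, the standardising SD, the number of groups, the N and the hypothesis. Say which hypothesis used three groups.
- Reconcile 0.23 in the synopsis with 0.23 to 0.27 in section 12.6.
- If a baseline covariate is meant to supply the missing power, specify it and justify its assumed correlation.
- Recheck the clinical-relevance statement (both places) and the appeal to preliminary data (section 12.6) against the corrected SFS effect.

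The cost is wording only, with no added participants and no change to conduct. The price is a less favourable stated detectable effect for SFS.

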## 1 BACKGROUND

Oxytocin (OT) is a neuropeptide produced in the hypothalamus that promotes affiliative behavior in animals, and is sometimes called “the bonding hormone.” The OT system has multiple interactions with dopaminergic reward pathways and this interplay likely mediates social behavior, permitting a range of social behaviors including trust, aggression, pair bonding and parenting.

## 2 STUDY RATIONALE

Oxytocin plays an important role in social behavior in mammals, including humans, increasing prosocial behavior and improving social cognition in healthy and autistic individuals. Evidence from animal and human models suggests that oxytocin may also play a specific role in the social deficits of schizophrenia. For example, peripheral oxytocin levels increase after a trust-related interaction in healthy subjects but not in patients with schizophrenia and this lack of response predicts negative symptom severity. Intranasal oxytocin administration has powerful prosocial effects and is extremely well tolerated. After intranasal oxytocin administration, healthy subjects gaze more at the information-rich eye region of faces and have better ToM. These data indicate that exogenous oxytocin selectively improves various aspects of social cognition and raises the possibility that exogenous oxytocin may be an effective adjunct treatment for improving social deficits in patients with schizophrenia. Indeed, several small recent preclinical studies and our own preliminary data demonstrate that oxytocin has positive effects on social cognition in schizophrenia, improving ToM. Furthermore, a recent, small clinical trial found that three weeks of intranasal oxytocin decreased negative symptoms of schizophrenia. While early work is promising, sample sizes are small and thus far there has been no integration of the observed behavioral effects of oxytocin with assessment of neural activity in schizophrenia.

### 2.1 Risk / Benefit Assessment

Potential side effects of intranasal OT include a runny, stuffy, or irritated nose. Studies using intranasal administration of OT of this dosage have reported no side effects. Pintocin® and Syntocinon® are synthetic and injectable forms of naturally occurring OT regularly used to induce uterine contractions in labor. The compounds may cause nausea and vomiting. No serious adverse effects have been demonstrated in studies examining intranasal administration of OT in numerous patient and healthy populations.

To minimize the risk of side effects and discomforts, study participants will be closely monitored for any adverse reactions to the intranasal administration of OT. The proper usage of an intranasal device will be demonstrated and explained to participants who may not be familiar with this type of drug administration. A medically licensed physician will be available by pager throughout the study.

---

The risks associated with intranasal OT use are minimal. However, all study participants will be monitored for any physical side effects and will be provided with additional rest, a drink of water, or the option to discontinue the study should these effects occur.

### **3 STUDY OBJECTIVES**

#### **3.1 Primary Objective**

The primary objective is to clarify how and in whom oxytocin improves social functioning in schizophrenia. The study will assess the effects of exogenous oxytocin on social functioning, as measured by the Social Functioning Scale (SFS). Neural activation patterns, as measured will be measured by fMRI rTPJ responses during well-characterized social cognitive tasks. This will help determine if acute fMRI rTPJ responses to single oxytocin administration predicts clinical responses to chronic oxytocin treatment in schizophrenia participants.

